### 7.5 Supportive Care Guidelines

Patients are allowed to receive full supportive care therapies concomitantly during the study. No other chemotherapy, immunotherapy, hormonal cancer therapy, radiation therapy, surgery for cancer, or experimental medications will be permitted while the patients are participating in

[REDACTED] J #: 081501

Title: A Phase 2 Randomized Discontinuation Trial in Patients with Hormone-Dependent Rising Prostate-Specific Antigen Progression After Local Therapy for Prostate Cancer Evaluating the Synergy of Metformin Plus Aspirin (PRIMA Trial).

PI: [REDACTED]

this study. It is not anticipated that patients will require significant supportive care. They may experience nausea and vomiting and the administration of antiemetic agents to control these symptoms would be acceptable.

### 7.6 Adherence/Compliance

- 7.6.1 Patients will be given a medication diary and instructed to initial it each time a dose is taken. Patients will also note the time the dose was taken, and if any side effects were experienced.
- 7.6.2 The desired level of compliance is  $\geq 90\%$ . Patients who cannot maintain this level of compliance will be removed from the study.

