#### **4.6 Duration of Follow-up**

For this protocol, all patients, including those who discontinue protocol therapy early, will be followed for response (or progression) and for survival for 1 year from the date of registration. All patients must also be followed through completion of all protocol therapy.

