### 7.3 Dose Modifications or Escalations

#### 7.3.1 Toxicity

Any Grade 3 or 4 non-hematologic adverse event, or Grade  $\geq 2$  renal toxicity, thought to be drug-related will lead to cessation of medications. If any of these occur, the patient will be removed from the study.

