## **16.2 Outcome Measures**

Difference in the stable PSA rates after 6 cycles of metformin and aspirin or placebo therapy will be calculated in patients who have received 4 cycles of open label treatment during the “run in phase”

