## **16.3 Sample Size and Statistical Analysis**

In this study, we hypothesize that patients with stable PSA after 4 cycles of open label treatment who are then treated with 6 cycles of metformin and aspirin will have a 40% rate of PSA or clinical progression compared to 80% rate of progression in patients treated with placebo. With 28 patients randomized to treatment or placebo the study will have 80% power to detect an increase in the proportion of patients with progression at 6 cycles from 40% to 80% with alpha =0.05. Assuming that approximately 10 patients progress prior to randomization, a total of 66 patients will be entered on this study.

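### Toxicity and compliance rules remove men from the study while section 4.6 keeps them in follow-up, and section 16 does not say how a removed randomised man counts, so the primary comparison may lose men after randomisation.

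*Combined protocol and SAP*

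**What the plan says.** **Removal.** Section 7.3.1 first stops the drugs for specified drug-related toxicity and then adds: "If any of these occur, the patient will be removed from the study". Section 7.6.2 sets a compliance target of at least 90% and continues: "Patients who cannot maintain this level of compliance will be removed from the study". Section 10 carries an off-study heading, but its lead-in is about how long treatment may continue. Its list includes adverse events and noncompliance.

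**Follow-up.** Section 4.6 says "all patients, including those who discontinue protocol therapy early, will be followed for response (or progression"), and for survival, for one year from registration. Footnote 7 of the section 6 schedule repeats this, with PSA every 12-16 weeks; on treatment it is every 4 weeks. Section 7.7 treats an emergency unblinding as off treatment with outcome follow-up continuing. Sections 7.3.1 and 7.6.2 have no such clause.

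**Analysis.** Section 16.2 says: "Difference in the stable PSA rates after 6 cycles of metformin and aspirin or placebo therapy will be calculated", in patients who had the 4 run-in cycles. Section 16.3 words the active-arm hypothesis for men "who are then treated with 6 cycles of metformin and aspirin". The synopsis refers the primary endpoint to randomised patients. None of these places states an analysis population or how a randomised man without 6-cycle status is counted. The only attrition allowance, 10 of 66, is for progression before randomisation.

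**The concern.** A site reading 7.3.1 or 7.6.2 could reasonably stop drawing PSA from a removed man; a site reading 4.6 would continue. Section 7.3.1 makes the first reading natural, because it orders cessation of the drugs and then, as a further step, removal from the study.

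The analyst faces the same gap. A removed man could be analysed on his later PSA, dropped, or counted as not progressed, and the plan does not choose. Only one arm takes active drug after randomisation, and the toxicity rule applies to events judged drug-related, so removal could be more frequent in the active arm. Counting such men as not progressed would then lower the active arm's progression rate. Dropping them would do so if the men removed were those more likely to progress. With 28 men per arm, a handful of removals matters.

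**Working it through.** **1. The plan's own figure.** Section 16.3 states: "With 28 patients randomized to treatment or placebo the study will have 80% power", for "progression at 6 cycles from 40% to 80% with alpha =0.05". It names neither the test nor the number of sides. For two proportions, two-sided:

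n = [1.960·√(2·0.6·0.4) + 0.842·√(0.4·0.6 + 0.8·0.2)]² / 0.4² = 22.3, so 23 per arm uncorrected.

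With the continuity correction, n' = (n/4)·[1 + √(1 + 4/(n·0.4))]² = 27.1, so 28 per arm. The stated size reproduces. Two-sided Fisher power at 28 per arm, by exact enumeration, is 82.3%. Fisher's test is used below as an assumption.

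**2. Removed men counted as not progressed, no true effect.** Removal rates are assumptions. The observed rate is p·(1 − removed fraction), with 28 per arm and p = 80% in both arms.

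| Removed, active vs placebo | Observed rates | Fisher rejection, two-sided |
|---|---|---|
| 0% vs 0% | 80% vs 80% | 2.0% |
| 10% vs 5% | 72% vs 76% | 3.3% |
| 20% vs 5% | 64% vs 76% | 10.8% |

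Of the 10.8%, 10.7 points favour the drug. With an uncorrected chi-square test the first and last rows are 4.8% and 16.9%. At a true 60% in both arms, Fisher goes from 2.6% with no removal to 5.7% at 20% versus 5% (48% vs 57%).

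**3. Removed men dropped, no true effect.** Suppose a fraction d of the active arm is removed, and these men have progression rate r. The observed active rate is (p − d·r)/(1 − d).

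- Removal unrelated to outcome (r = p): at p = 60% and d = 20% (22 vs 28 men), Fisher rejection is 3.9%, so there is no inflation.
- Worst case (r = 100%), p = 60%: d = 10%, 20% and 30% give active rates of 55.6%, 50.0% and 42.9%, with rejection rates of 4.2%, 9.3% and 18.5%.
- Worst case, p = 80%, d = 20%: (0.80 − 0.20)/0.80 = 75%, with rejection 5.1%.

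**4. Power when men are dropped.** With 20% versus 5% removed, 22 vs 27 men remain. Fisher power at 40% vs 80% is 80.0%, against 82.3% with nobody lost.

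**5. Power when all 56 are analysed.** Assume a fraction d of active men stop drug and progress at the placebo rate of 80%. The active rate is 0.4·(1 − d) + 0.8·d.

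| d | Active rate | Fisher power, 28 per arm | n per arm for 80% power (corrected formula) |
|---|---|---|---|
| 10% | 44% | 73.6% | 33 |
| 20% | 48% | 63.2% | 41 |
| 30% | 52% | 51.6% | 51 |

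**6. Is the 6-cycle outcome inside the follow-up window?** Four run-in cycles plus six randomised cycles of 4 weeks end at about week 40 (16 + 24), within the one-year follow-up. But once a man is off treatment, PSA is every 12-16 weeks and no draw is tied to 24 weeks after randomisation. His 6-cycle status can be missed or found late.

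**The case against.** A reader might infer that the plan specifies a completer analysis that will lose men selectively by arm. The documents do not support that.

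- Section 4.6 and footnote 7 require progression follow-up after early stopping, and the lead-in to section 10 suggests that removal is sometimes used loosely for stopping drug.
- The synopsis speaks of randomised patients. Section 16.2 restricts the population only to men who had 4 run-in cycles, and its reference to 6 cycles can be read as a time point. The as-treated phrase in 16.3 sits in a power hypothesis.
- Pill burden does not explain differential loss: the control arm takes placebo metformin and placebo aspirin tablets (sections 4.3 and 12.3).
- Every randomised man has already been through four cycles on both drugs under the same removal rules, so many who could not tolerate or comply should have left before randomisation.
- No removal rates are given. The larger inflation needs a gap such as 20% versus 5% together with counting removed men as not progressed, and the plan prescribes neither.

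All of this stands, and it reduces the point from a certain loss to a possible one. It does not settle the matter. Section 4.6 governs data collection and cannot fix the denominator in section 16, and it contradicts 7.3.1 and 7.6.2 as worded. The synopsis does not say how a removed man is counted.

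**Conclusion.** The point holds as an unresolved contradiction between removal and follow-up, joined to a missing analysis population and a missing rule for absent 6-cycle status. Literal use of the removal rules may cost the primary comparison randomised men, and drug-related toxicity could make that loss unequal.

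The size depends on assumptions that the documents cannot confirm. Counting removed men as not progressed leaves the false-positive rate small at 10% versus 5% removal but raises it about fivefold at 20% versus 5% (10.8% / 2.0% = 5.4). Dropping men causes bias only if removal is related to outcome; the 9.3% figure is a worst case. Lost power from dropping men is minor, and the stated sample size is not in error.

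**What to change.** 1. Reconcile 7.3.1, 7.6.2 and section 10 with 4.6 and footnote 7, so that removal does not end outcome follow-up. The criteria for stopping drug stay as they are.
2. State in 16.2 and 16.3 that every randomised man is analysed in his assigned arm, for progression by 6 cycles (24 weeks) after randomisation.
3. Add a PSA at that time point for men off drug.
4. State how missing 6-cycle status is handled, and add a sensitivity analysis counting such men as progressed. Censoring at removal would itself assume that removal is unrelated to outcome, so it should not stand alone.

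The cost is wording, one sensitivity analysis and one PSA draw for men off drug. The real price is dilution: the sponsor should know before analysis that power with all 56 men falls to about 63% if 20% of active men stop and progress at 80%.

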### 7.7 Emergency Unblinding procedure

**Emergency Unblinding:** In the event of an emergency, please contact [REDACTED] PharmD, FCCP, BCOP, Monday through Friday between 9:00am and 5:00pm Eastern Time. For unblinding outside of these hours, please contact [REDACTED] for further instruction. **Remember, this is only in the event of an emergency. Please note that, if a patient is emergently unblinded, they are considered to be off treatment, but should continue to be followed for outcome evaluations.**

## 8. Toxicity Monitoring and Adverse Event Reporting

All patients who receive one dose of protocol therapy will be evaluable for toxicity. Each month the treating physician will fully assess the patient's condition with respect to possible treatment related toxicities. All adverse events, whether observed by the physician or reported by the patient, occurring during the active portion of therapy, or up to 30 days after the last dose of treatment will be graded by a numerical score according to the NCI's Common Terminology Criteria for Adverse Events (CTCAE), Version 4.0 (<http://ctep.cancer.gov/reporting/ctc.html>) and recorded in the patient's medical record. Toxicities will be reported as outlined in the study data capture plan. The type, grade, and toxicity attribution information will be recorded.

A preexisting condition is one that is present at the start of the study drug. A preexisting condition should only be recorded as an adverse event if the frequency, intensity, or the character of the condition worsens during the study period.

### 8.1 Adverse Event Reporting Requirements

An adverse experience is defined as any unintended or abnormal clinical observation that is not of benefit to the patient. Either the condition was not present prior to exposure to the study therapy, or it has worsened in intensity or frequency following exposure to the study therapy.

All "unexpected" (defined below) and/or "serious" (defined below) adverse events occurring during the active portion of therapy, or up to 30 days after the last dose of treatment, will be reported to OHRS at [REDACTED]. Events will be promptly reported, in writing, to the local IRB. If a death occurs the IRB will be notified within 24 hours of initial receipt of information. All other SAEs must be reported to the IRB within three to ten days of initial

Protocol Version 8.0 12/01/2017

Title: A Phase 2 Randomized Discontinuation Trial in Patients with Hormone-Dependent Rising Prostate-Specific Antigen Progression After Local Therapy for Prostate Cancer Evaluating the Synergy of Metformin Plus Aspirin (PRIMA Trial).

PI: [REDACTED]

receipt of information. Written follow-up reports are required when additional information is obtained to fully characterize the event. Copies of each report sent to the IRB will be kept in the study regulatory file.

In addition to reporting to the local IRB, reporting to external bodies such as the FDA must also occur.

### **8.2 Reporting SAEs**

The PI shall notify the FDA of any adverse experience associated with the use of the drug that is both serious and unexpected, as soon as possible and in no event later than 15 calendar days after the PI's discovery of the event. Each written notification may be submitted on FDA Form MedWatch 3500A <http://www.fda.gov/medwatch/safety/3500a.pdf> (fax # [name]).

The PI shall also notify the FDA by telephone or by facsimile transmission of any unexpected fatal or life-threatening experiences associated with the use of the drug, as soon as possible but no later than 7 calendar days from the PI's discovery of the event information.

### **8.3 Definition of Serious Adverse Events (SAEs)**

A serious adverse event (experience) is one occurring at any dose level that results in any of the following outcomes:

- Death
- Life-threatening- immediate risk of death from the reaction.
- Requires inpatient hospitalization or prolongation of existing hospitalization.
- Results in persistent or significant disability/incapacity.
- Results in a congenital anomaly/birth defect.
- Requires intervention to prevent one of the outcomes listed in this definition.

The definition of serious adverse event (experience) also includes *important medical events*. Medical and scientific judgment will be exercised in deciding whether expedited reporting is appropriate in other situations, such as important medical events that may not be immediately life-threatening or result in death or hospitalization but may jeopardize the patient or may require intervention to prevent one of the other outcomes listed in the definition above. These events will usually be considered serious. Examples of such events are intensive treatment in an emergency room or at home for allergic bronchospasm; blood dyscrasias or convulsions that do not result in hospitalization.

### **8.4 Definition of Related Adverse Event**

There is a reasonable possibility that the drug caused the adverse experience. That is, the event is judged by the investigator to be possibly, probably or definitely related to the treatment.

### **8.5 Definition of Unexpected Adverse Event**

Any adverse drug experience and/or specificity or severity, that is not included in the current investigator's brochure and/or package insert.

Protocol Version 8.0 12/01/2017

## 9. Treatment Evaluation/Criteria for Response

### 9.1 Biochemical Response/progression:

Criteria for response are indicated in section 4.

### 9.2 Clinical Progression

The appearance of new lesions on examination or radiographs (CXR, CT scan, MRI scan, or bone scan) will be evidence for clinical progression. The development of symptoms consistent with metastatic disease (i.e., bone pain) with a concurrent increase in serum PSA from baseline will also be grounds for evaluating for clinical progression via radiographs.

### 9.3 Survival

Survival will be measured starting from the date of entry on study. Patients will be followed for one year after initial enrollment.

## 10. Removal of Patients from Study/Off Study Criteria

In the absence of treatment delays due to adverse events, treatment may continue until one of the following criteria applies:

- a) Intercurrent illness that prevents further administration of treatment,
- b) Unacceptable adverse event(s),
- c) In the event of any drug-related life-threatening toxicity or laboratory abnormality the patient will be withdrawn from further treatment,
- d) Patient decides to withdraw from the study,
- e) Noncompliance with treatment plan,
- f) General or specific changes in the patient's condition that render the patient unacceptable for further treatment in the judgment of the investigator, or
- g) Protocol violation - any patient found to have entered this study in violation of the protocol might be discontinued from the study at the discretion of the Principal Investigator.
- h) PSA progression after at least 30 days of treatment (see Section 4.5).

## 11. Laboratory Evaluations and Correlative Studies

These analysis are optional however, every effort should be made to collect samples for analysis. Metformin treatment has been reported to not only lower blood glucose but also to reduce serum IGF-1 levels and insulin levels [68]. IGF-1 plays an important role in both cellular mutagenesis and human malignancies. Aspirin may inhibit the activation of NFκB, which further suppresses the expression of tumor necrosis factor-alpha (TNF- $\alpha$ ), interleukin 6 (IL-6) and IL-1 $\beta$  [54]. Therefore, in this proposed study, we are particularly interested in determination of the serum factors, insulin, IGF-1, IL-6, IL-1 $\beta$ , and TNF- $\alpha$ . Additionally salicylate levels will be measured at baseline and through Cycle 5. Salicylate levels will NOT be collected after Cycle 5..

- At baseline, cycle 2, cycle 4, cycle 5, cycle 6, cycle 8, cycle 10 and end of treatment cycle, 7.5mL of blood will be collected in a red top tube. Serum will be distributed into eppendorf tubes and frozen for batched analysis by ELISA.
- To monitor aspirin levels in patients, salicylate levels will be monitored at baseline and every other cycle.

Title: A Phase 2 Randomized Discontinuation Trial in Patients with Hormone-Dependent Rising Prostate-Specific Antigen Progression After Local Therapy for Prostate Cancer Evaluating the Synergy of Metformin Plus Aspirin (PRIMA Trial).

PI: [REDACTED]

### **11.1 Collection and Handling Procedures**

Blood specimens will be handled by the Cancer Institute's Tissue Analytical Service (TAS).

#### **Documentation**

Please have the name, address and the appropriate laboratory or office phone number of the institution that the patient specimens were shipped from. For any questions relating to shipment of samples please call [REDACTED]

### **11.2 Storage & Future Use of Specimens**

Subjects will provide consent for retention and future use of specimens. At the time of consent, subjects will be informed that they may also refuse permission for future research use of their specimens without affecting their participation in the study or care by the health provider.

Specimens will be collected and processed following standard Biospecimen Repository Service (BRS) procedures. All specimens will be de-identified and given a unique BRS#. Only pathological information for each corresponding blood samples will be recorded.

Specimens will be stored at [REDACTED]  
Service (BRS), Room # 2050.

Specimens will be labeled by a unique identification number and initials only; there will be no other link to the subject. This link, along with data and health information collected for the main protocol, will be retained for a period of 6 years in the Office of Human Research Services (OHSR) on behalf of the principal investigator.

## **12.**

### **Pharmaceutical Information**

#### **12.1 Metformin**

**Product Description:** tablet

**Product Name:** Metformin

**Product Dosing:** 1000mg BID.

**How Supplied:** commercial supply and distributed by CINJ pharmacy

**Storage Requirements/Stability:** room temperature

**Route of Administration:** Oral

**Adverse Reactions:** Most common: diarrhea, nausea, vomiting, flatulence, asthenia, indigestion, abdominal discomfort and headache.

Prot [REDACTED]

3B  
Approved Date: [REDACTED]  
Expiration Date: 1/15/2020

Title: A Phase 2 Randomized Discontinuation Trial in Patients with Hormone-Dependent Rising Prostate-Specific Antigen Progression After Local Therapy for Prostate Cancer Evaluating the Synergy of Metformin Plus Aspirin (PRIMA Trial).

PI: [REDACTED]

## 12.2 Aspirin

**Product Description:** tablet

**Product Name:** Aspirin

**Product Dosing:** 81mg.

**How Supplied:** commercial supply and distributed by [REDACTED] Pharmacy

**Storage Requirements/Stability:** room temperature

**Route of Administration:** Oral

**Adverse Reactions:** Most common: Rash, gastrointestinal ulcerations, abdominal pain, cramping, nausea, gastritis, lactic acidosis, and bleeding.

## 12.3 Aspirin and Metformin Placebo

Aspirin and metformin placebo tablets will be produced by the Rutgers School of Pharmacy and distributed by the [REDACTED] Pharmacy.

## 13. Data Collection and Records to be Kept

### 13.1 Case Report Forms

A subset of the [REDACTED] CRFs, in electronic format, will be utilized. Completion of the electronic CRFs (eCRFs) will be done in accordance with the instructions in a study specific data capture plan. All eCRFs will be completed by clinical research coordinators of OHRS at the [REDACTED]. The eCRFs will be maintained in a confidential format in Oncore®.

### 13.2 Data Submission Timeline and Forms

Completion of eCRFs will occur in accordance with NCI guidelines. Baseline (pre-study) eCRFs (e.g., enrollment, medical history, concomitant medications, disease assessment, etc.) will be completed no later than 14 days after the start of treatment. Treatment eCRFs (e.g., drug administration, adverse events, chemistries, etc.) will be completed no later than 14 days following each cycle of treatment. Off-treatment information (e.g., follow-up, best response, etc.) will be completed no later than 14 days after the end of protocol treatment.

### 13.3 Research Charts

A research chart is maintained at OHRS for each patient enrolled. Copies of significant study source documents will be maintained in the research chart. Examples of source document copies that will be maintained in the research chart include: signed informed consent form, documents that verify eligibility and treatment and documents that verify Grade 3-4 adverse events and response. This information will be updated on a prospective basis and will be confidentially maintained in OHRS.

Protocol Version 8.0 12/01/2017

Title: A Phase 2 Randomized Discontinuation Trial in Patients with Hormone-Dependent Rising Prostate-Specific Antigen Progression After Local Therapy for Prostate Cancer Evaluating the Synergy of Metformin Plus Aspirin (PRIMA Trial).

PI [REDACTED]

